This is a randomized, double-blind, placebo-controlled, two-arm parallel, single-center study. One hundred subjects (50 in each arm) will be enrolled. Subjects, between the ages 18 and 65, undergoing laparoscopic gastric bypass or sleeve gastrectomy under general anesthesia will be screened for eligibility to participate in the study. Subjects will be screened, recruited and consented during the preadmission visit prior to surgery. Eligible subjects will be randomized to one of the two treatment group in a 1:1 ratio to receive either IV ketamine (0.4mg/kg) or matching placebo. Both men and women will be recruited, and there is no limitation as to racial and ethnic origin.

Participation in the study will not alter the patient's surgical or anesthetic care, post-anesthetic care, or care on the floor. In the PACU, patients, if deemed medically stable by the study physician, will receive either 0.4mg/kg IV ketamine or placebo. All patients will also receive standard post-anesthetic monitoring and care, as well as routine care after transfer out of the PACU. There is no restriction on the use of other analgesics throughout the hospital stay. Patients are followed until the date of discharge, and endpoints (see below) are collected from patient reports as well as from medical charts. During their hospital stay (and once after their discharge from the hospital), patients will fill out five questionnaires which provide estimates of their postoperative pain control, mood and function, and quality of postsurgical recovery.

Patients will be randomized using a block randomization code for assigning 100 subjects to two groups. In Excel we generated 100 random numbers. In the next column we inserted multiple copies of the sequence PCPC where p= "placebo" and c = "control", forming 25 blocks. Then we sorted the random numbers in each 4 subject block, including the assignment letters (P, C) in the sort. The remaining list of Ps and Cs is the randomization.

To check the balance, we then did running counts of the cumulative repeats of "p" and "c" and "p - c". The tally for each totaled 50 and the two groups were always within 2 counts of being perfectly balanced, which met our goal. The list can be extended at will to accommodate screening failures.

Randomization lists will be sent to the pharmacy who will then be able to distribute the study drug/placebo as patients are enrolled and undergoing surgery, and the remainder of the study staff will be blinded.

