An additional component of the study, which is entirely optional, is to obtain patient serum samples (about two teaspoons) in the operating room and 15 minutes and 4 hours after ketamine infusion. We will use these samples to assess levels of IL-1, IL-6, TNF- α , and BDNF, which are markers for pain. In addition, with patient consent, we will also store serum samples for future research use to measure other cytokines and neurotrophic factors and molecular markers associated with pain and depression.

Study site: Tisch Hospital

Outcome measures

Primary outcome measure: scores on the following questionnaires: 1) The Beck Depression Inventory (BDI); 2) Visual Analog Scale (VAS) score; 3) McGill's short form; 4) QoR-15 form; and 5) Montgomery-Asberg Depression Rating Scale (MADRS). The BDI and MADRS provide assessments for mood and function, VAS and McGill's assess pain, and QoR-15 assesses patient's overall satisfaction with postoperative recovery.

After consent is achieved in the pre-admission clinic prior to surgery, patients will be asked to fill out BDI, MADRS and QoR-15 forms to establish baseline scores. The BDI, MADRS will be filled out on postoperative days (POD) 0 after the infusion of ketamine, and BDI, MADRS and QoR-15 forms will be repeated on POD1, 2 and 7. McGill's short form will be filled out prior to discharge from the PACU and on POD 1, 2 and 7. VAS will be filled prior to PACU discharge, and every day while patient is in the hospital and on POD 7. VAS is a routine part of hospital care and will be administered daily whether a patient is enrolled in the study or not. If a patient has been discharged prior to POD2 or 7 (patients typically are discharged on POD2 or 3 in our practice), then a member of the study team will contact the patient by telephone to fill out these questionnaires.

Secondary outcome measures: 1) length of stay during hospitalization; 2) opioid usage per hour during the PACU stay before and after ketamine infusion; 3) opioid usage per day throughout the hospital stay; 4) time to out of bed to chair (OOB); 5) spirometry use 4 hours after the termination of ketamine infusion; 5) anti-emetic use in the PACU.

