Musculoskeletal: Musculoskeletal side effects have included enhanced skeletal muscle tone manifested by tonic and clonic movements sometimes resembling seizures.

Local: Local side effects have included pain and exanthema at the injection site.

Dermatologic: Dermatologic side effects have included transient erythema and/or morbilliform rash.

Psychiatric: Psychiatric side effects have included anxiety, euphoria, dysphoria, illusions, hallucinations, flashbacks, blunted affect, catatonia and psychotic episodes.

Neurologic: Impaired attention/memory/judgment, disorientation, delirium, diplopia, blurred vision.

Urinary: Increased urinary output; rarely cystitis.

Duration of Effects: Onset of effects is within seconds if smoked, 1-5 minutes if injected, 5-10 minutes if snorted and 15-20 minutes if orally administered. Effects generally last 30-45 minutes if injected, 45-60 minutes if snorted, and 1-2 hours following oral ingestion.

Tolerance, Dependence and Withdrawal Effects: In long-term exposure, high tolerance, drug craving, and flashbacks are described. Little evidence of a physiological withdrawal syndrome unless abrupt discontinuation in chronic users.

Drug Interactions: Lorazepam may decrease ketamine-associated emotional distress but does not decrease cognitive or behavioral effects of ketamine. Acute administration of diazepam increases

the half-life of ketamine. Lamotrigine significantly decreases ketamine-induced perceptual abnormalities, but increases the mood elevating effects. Haloperidol may decrease impairment by ketamine in executive control functions, but does not affect psychosis, perceptual changes, negative schizophrenic-like symptoms, or euphoria. Alfentanil is additive to ketamine in decreasing pain and increasing cognitive impairment. Physostigmine and 4-aminopyridine can antagonize some pharmacodynamic effects of ketamine.

Absolute contraindications to IV ketamine are age <3 months and schizophrenia. Relative contraindications include increased ICP, glaucoma, or acute globe injury. Caution is suggested in patients with cardiovascular illness, porphyria, or thyroid disorder.

Human subject

This study will be carried out under the guidelines of the New York University School of Medicine, Institutional Review Board (IRB), the NYU-HHC CTSI, and in accordance with the Guide for the Care and the Use of Laboratory Subjects as adopted and promulgated by the US National Institutes of Health.

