Sample Size Justification: Previous studies on the antidepressant effects of ketamine on depressed patients typically yield a mean difference in psychometric measures of 40%, with a standard deviation of roughly 40% as well. Power analysis yields $n = 50$ patients in each arm. This will allow for us to detect a true difference in the mean value of our outcome variable of $\pm 22.5\%$ with a probability (power) of 0.8. The type I error probability associated with this test of the null hypothesis that the population means of the ketamine versus control groups are equal is 0.05.

Statistical Analysis: For this study, descriptive statistics will be performed for all data and subgroups as needed:

- 1) Outcome tests (see above), N (%) for each category, showing absolute values, absolute

and percent differences, stratified by treatment etc.

- 2) Demographics showing continuous parameters (age, height, weight, etc.) as mean + SD; categorical parameters, as N (%); all also stratified by treatment.

Analysis of variance (ANOVA) test with repeated measures will be performed to determine within-patient effects (time) and between patient effects (treatment) on outcome measures. Pearson correlation will be used to assess relationships between continuous variables, and Spearman's Rho will be used for ranked data. For non-normally distributed, the Kruskal-Wallis test will be used for global significance, and Mann Whitney for subsequent pairwise comparisons.

Exploratory analysis will fit continuous (VAS score, length of stay in the hospital) and categorical (ordinal outcome data) to a Logistic Regression model which predicts the treatment bivariate (IV ketamine or placebo).

Interim Data analysis: An interim data analysis will be performed after a total of 50 patients have completed the study. An analysis of primary and secondary endpoints will be analyzed, and if the primary endpoints are met, we will opt to terminate the study.

DATA SAFETY AND MONITORING PLAN

Timeline

- 1) Estimated start date: Sept 1, 2013
- 2) Estimated time for start-up: 2 months
- 3) Time allotted for enrollment: 2 years
- 4) Estimated study end date: August 30, 2015

Data acquisition and management

The research material obtained from human subjects in this proposed study will be collected solely for research purposes. It will be as follows:

- a. *Clinical information* obtained by medical history, questionnaires and interviews.

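### The first VAS and McGill scores have no fixed time after the infusion and are bounded only by PACU discharge, so the arms may be compared at different times since drug

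*Combined protocol and SAP*

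**What the plan says.** The protocol's Outcome measures section makes five questionnaires primary, among them VAS and McGill for pain. For the first postoperative pain scores it says that "McGill's short form will be filled out prior to discharge from the PACU and on POD 1, 2 and 7" and that "VAS will be filled prior to PACU discharge". After that, VAS is taken daily in hospital and on POD 7. Neither sentence gives an interval after the study infusion, a window, or a requirement that the score follow the infusion. I find no instruction to record the time of scoring.

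The same section and the paragraphs after it tie other early measures to the infusion. BDI and MADRS on POD 0 come after it. Serum is drawn 15 minutes and 4 hours after its end, and spirometry is assessed at 4 hours.

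On rescue medication, Overall study design and plan says: "There is no restriction on the use of other analgesics throughout the hospital stay". Intervention Administration allows an infusion of any length under 60 minutes, refers to the standard PACU protocol, and lists sedation, confusion and dizziness among possible side effects. No PACU discharge criterion is given anywhere. PACU opioid use per hour, before and after the infusion, is a secondary outcome.

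**The concern.** Leaving the PACU is an event after randomization, and pain, opioid use and sedation can all move it. A score limited only by that event need not be taken at the same time since drug in the two arms. A patient in more pain can receive more opioid, stay longer and be scored later, when pain has fallen. A patient kept back by sedation can also be scored later, for a reason that has nothing to do with analgesia.

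This is the pain score nearest to a single-dose drug, in two primary measures. The repeated-measures ANOVA in Statistical Analysis would treat the PACU score as one common time point when it may not be.

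**Working it through.** **1. The plan's own figure.** Inputs from Sample Size Justification: detectable difference 22.5%, SD 40% ("with a standard deviation of roughly 40% as well"), type I error 0.05 (taken as two-sided from the plus/minus sign), power 0.8. The normal formula is n per arm = 2(1.96 + 0.842)² × (40/22.5)² = 2 × 7.85 × 3.16 ≈ 49.6, so 50. The stated size is reproduced, and 50 per arm gives power 0.803. The standardised difference is 22.5/40 = 0.5625. Nothing below changes N.

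**2. Direction of the bias.** Suppose pain falls at s points per hour in both arms after the infusion, and ketamine lowers it by δ. If the mean scoring times are T_P (placebo) and T_K (ketamine), the observed difference is about

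δ − s × (T_P − T_K).

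- Placebo scored later: attenuated.
- Ketamine scored later: inflated.
- Equal times: unchanged.

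**3. Size if discharge depends on pain and the score is taken at discharge.** Every input here is an assumption except the standardised effect: 0–100 scale, placebo mean 60, SD 20, effect 0.5625 × 20 = 11.25 points, pain falling 5 points per 15 minutes (s = 20 per hour), release at the first 15-minute check at or below a pain limit. The comparator is the score at the first check.

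| Pain limit for discharge | T_P − T_K (min) | Formula in step 2 | Simulated difference | Share of fixed-time difference | Power, this score, 50 per arm |
|---|---|---|---|---|---|
| 30 | 30.4 | 1.1 | 0.9 | 9% | 21% |
| 40 | 27.4 | 2.1 | 2.1 | 19% | 40% |
| 50 | 22.4 | 3.8 | 3.9 | 35% | 57% |
| 60 | 15.5 | 6.1 | 6.1 | 55% | 69% |
| 70 | 9.1 | 8.2 | 8.1 | 74% | 75% |
| none | 0 | 11.25 | 11.0 | 100% | 80% |

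For example, at a limit of 40: 11.25 − 20 × 27.4/60 = 2.1. Power falls less than the difference does because a pain limit also narrows the spread of scores.

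**4. A second set of assumptions.** 0–10 scale, placebo mean 5.5, SD 2, ketamine 1.5 lower, pain falling 0.75 or 1.5 points per hour, reading noise SD 0.7, pain limit 3, 4 or 5, checks every 15 minutes. I re-ran this and it reproduces.

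- Fixed 30 minutes: difference 1.45 points (0.71 SD), power 0.94.
- Scored at discharge: 0.30 to 0.82 points, that is 0.30/1.45 = 21% to 0.82/1.45 = 57%; 0.40 to 0.62 SD; power about 0.50 to 0.87.
- Scored at a random check up to discharge: 0.96 to 1.22 points, or about two-thirds to 84%; power 0.82 to 0.92.
- Discharge unrelated to pain: 1.46 points, no loss.
- Discharge unrelated to pain, but no ketamine patient leaves before 30 minutes: 1.65 to 1.81 points, which is inflated.
- That delay together with a pain limit: 0.41 to 0.97 points, still attenuated.

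These powers are for the first score alone. The effect on the repeated-measures result was not computed.

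**The case against.** A reader might infer that PACU discharge waits for acceptable pain, so that both arms are scored at similar pain by construction. The documents do not support this. They refer only to standard care and state no discharge criterion. Even where a pain limit is assumed, the scores do not become equal: 21% to 57% of the difference remains in step 4.

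A reader might also infer that the bias is known to run toward no effect. The side effects listed in Intervention Administration could hold ketamine patients back, and step 4 shows the difference inflated when that happens without a pain limit.

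The wording sets a latest time, not the moment of scoring. Scores taken earlier lose much less, as the random-check result shows. That reduces the likely size, but it also concedes that the timing is open, even to the point of allowing a score before the infusion.

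It is tempting to add that a discharge score misses the drug's effect because the protocol says "Effects generally last 30-45 minutes if injected". That line sits among smoked, snorted and oral use and describes effects in general, not analgesia after an infusion. It is weak support, and the simulations do not use it.

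Finally, the study rationale is about long-lasting analgesia. The later scores address that and follow the calendar: POD 1, 2 and 7 for McGill, daily in hospital and POD 7 for VAS. Hourly PACU opioid use captures part of any early analgesia. All of this stands and limits the point to one time point. It does not repair that score, which remains part of two primary measures.

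**Conclusion.** The point holds in a conditional form and is a cheap improvement. The first VAS and McGill scores have no defined time after the infusion and are bounded only by an event that treatment can affect.

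- If discharge depends on pain control, the early difference is attenuated. Under the assumptions shown, 9% to 74% remains when scoring coincides with discharge, and about two-thirds to 84% when it falls at a random check up to discharge.
- If ketamine side effects delay discharge, the difference can be distorted the other way.
- If discharge is unrelated to both pain and arm, there is no bias.

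The documents do not show which case applies. The pain levels, slopes and limits are all assumptions. The later pain scores are not affected, and no claim is made that the trial's overall pain conclusion is lost.

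**What to change.** In Outcome measures, replace the two phrases that tie the first McGill and VAS scores to leaving the PACU with one fixed assessment time after the end of the study infusion. Give it a narrow window, use it for both forms, and apply it whether or not the patient is ready to leave. The plan already works this way for serum and spirometry. Record the times of infusion end, scoring and PACU discharge. In Statistical Analysis, name this score as the PACU time point in the repeated-measures analysis, and say that it will be read alongside PACU opioid use.

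The cost is a wording change and three recorded times. There is no extra visit, no change in N and no change in care. The small downside is that some patients may be drowsier at the fixed time than they would be at discharge.

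### VAS readings on POD3–6 exist only for patients still in hospital, and the repeated-measures ANOVA does not exclude them; a pre-infusion VAS and the timing of the PACU pain scores also need to be stated

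*Combined protocol and SAP*

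**What the plan says.** VAS and the McGill short form are two of the five primary questionnaires (Outcome measures). Their schedules differ from those of the other three.

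- **Baseline.** Before surgery, "patients will be asked to fill out BDI, MADRS and QoR-15 forms to establish baseline scores". VAS and McGill are not in that list.
- **Day of surgery.** "The BDI, MADRS will be filled out on postoperative days (POD) 0 after the infusion of ketamine". For the pain scales, the text says "McGill's short form will be filled out prior to discharge from the PACU and on POD 1, 2 and 7" and, for VAS, "VAS will be filled prior to PACU discharge, and every day while patient is in the hospital and on POD 7". Neither PACU score is placed relative to the infusion, which is itself given in the PACU.
- **Routine charting.** "VAS is a routine part of hospital care and will be administered daily whether a patient is enrolled in the study or not".
- **After discharge.** The section notes that "patients typically are discharged on POD2 or 3 in our practice". If discharge comes before POD2 or POD7, "then a member of the study team will contact the patient by telephone to fill out these questionnaires".
- **Expected effect on stay.** The Study Rationale hypothesises that ketamine leads to earlier discharge. Length of stay is a secondary outcome.
- **Analysis.** The Statistical Analysis section, repeated in the data safety and monitoring plan, applies a repeated-measures ANOVA with time and treatment effects to the outcome measures. It names no days, no baseline covariate and no rule for missing values.

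**The concern.** For BDI, MADRS, QoR-15 and McGill the schedule itself fixes the days. VAS alone runs on for as long as the patient stays. POD7 is set for everyone, and POD1 and POD2 are in effect covered by inpatient readings or the telephone call. A POD3–6 value, however, exists only if the patient has not gone home. An analyst who follows the schedule as written could enter those days in the ANOVA. The result would then depend on an unstated choice. Complete-case analysis discards discharged patients. Available-case analysis compares arms that have been selected by a post-randomisation stay that treatment is expected to change.

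Two smaller gaps concern the start of the VAS series. Without a designated pre-infusion score there is nothing to adjust for, although the score is cheap to obtain from routine charting. And because the PACU pain scores are not tied to the end of the infusion, the text does not rule out a score taken before treatment.

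**Working it through.** **Inputs from the plan (Sample Size Justification):** difference 22.5, SD 40, 50 per arm, alpha 0.05 (two-sided assumed), power 0.8. These figures come from antidepressant studies and are borrowed here for VAS. The documents give no pain SD, no correlations and no share of patients in hospital by day, so those are assumptions shown as ranges.

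**1. The plan's own figure.** d = 22.5/40 = 0.5625. Power = Φ(d·√(50/2) − 1.96) = Φ(2.813 − 1.96) = 0.803. The noncentral t gives 0.795. The stated 50 per arm is reproduced and is not in dispute.

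**2. POD3 entered, complete cases, equal discharge in both arms.** Take the mean of five occasions (PACU, POD1, 2, 3, 7), a constant effect, and an assumed within-patient correlation of 0.5. The variance of the mean relative to one occasion is (1 + 4 × 0.5)/5 = 0.6, so d = 0.5625/√0.6 = 0.726. Noncentral t power:

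| Share still in hospital on POD3 | n per arm | Power |
|---|---|---|
| 100% | 50 | 0.95 |
| 70% | 35 | 0.85 |
| 50% | 25 | 0.71 |
| 30% | 15 | 0.48 |

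For comparison, leave POD3 out and keep all 50 per arm over the four fixed occasions. The variance factor is (1 + 3 × 0.5)/4 = 0.625, d = 0.5625/√0.625 = 0.712, and power is 0.94. Dropping POD3 therefore costs almost nothing.

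**3. POD3 entered, available cases, no true effect on pain.** Let r be the correlation between pain and the tendency to stay, and p the share still admitted. Mean pain among those remaining is r·φ(z_p)/p in SD units, so the spurious difference (ketamine minus placebo) is r·[φ(z_k)/p_k − φ(z_p)/p_p]. The values of φ(z)/p are 1.159, 0.966, 0.880 and 0.798 at p = 0.30, 0.40, 0.45 and 0.50. With 50% of placebo patients admitted:

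| Ketamine share admitted | r = 0.3 | r = 0.5 | Divided by five occasions |
|---|---|---|---|
| 30% | 0.108 | 0.181 | 0.022 to 0.036 |
| 40% | 0.050 | 0.084 | 0.010 to 0.017 |
| 45% | 0.025 | 0.041 | 0.005 to 0.008 |
| 50% | 0 | 0 | 0 |

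The sign is against ketamine: the patients who remain on the arm that goes home sooner are the more painful ones.

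**4. Pre-infusion VAS as covariate, one time point, 50 per arm.** The residual SD is 40·√(1 − ρ²). Normal-approximation power rises from 0.80 to 0.81 (ρ = 0.1), 0.82 (0.2), 0.84 (0.3) or 0.90 (0.5). With the noncentral t and one degree of freedom lost to the covariate, 0.795 becomes 0.799, 0.811, 0.831 or 0.895.

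**5. PACU score taken before the infusion.** Such a score carries no treatment effect, so a share s of them shrinks the PACU difference to 22.5 × (1 − s). At s = 10%, 25% or 50% the difference is 20.25, 16.9 or 11.25, and power at that time point is 0.72, 0.56 or 0.29. These shares are purely illustrative.

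**The case against.** The strongest reply is that the harm is conditional. The plan never says POD3–6 enter the ANOVA. POD1, POD2 and POD7 are common to all five forms, and a sensible analyst would use them. If so, neither the loss of patients nor the selection arises. Listwise deletion is also an assumption, because the plan gives no missing-data rule. Both points stand. They make this a matter of specification, not an error already built into the result.

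A reader might go further in four ways that the documents do not support.

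- **That the lost power is worse still.** Computed for POD3 alone, complete-case power would be 0.64, 0.50 or 0.32. The plan specifies repeated measures, so the five-occasion figures above are the fairer ones.
- **That the VAS comparison is seriously biased.** Averaged over five occasions the bias is at most 0.036 SD, or 0.036/0.5625 = 6% of the design effect. Reaching even that needs an assumed 50% against 30% inpatient split and a pain–stay correlation of 0.5. It works against ketamine, not for it.
- **That the missing baseline biases the result.** Allocation is randomised, so it does not. It gives up precision, and only recovers it if a covariate-adjusted analysis is also specified. A routine pre-infusion reading may already be charted, and a figure just before Intervention Administration is not shown and could hold a schedule.
- **That PACU pain is scored before treatment.** After the infusion is the natural reading of a score due before PACU discharge. Nothing suggests otherwise; the text merely does not say so, as it does for BDI and MADRS.

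**Conclusion.** The point holds as a gap in specification that is cheap to close. The VAS schedule produces stay-dependent readings on a primary outcome, and the ANOVA does not exclude them. If POD3 is entered, complete-case power falls from 0.95 to between 0.85 and 0.48 for 70% to 30% still admitted. Available-case bias is 0 to 0.18 SD on POD3, or 0 to 0.04 SD over five occasions, against ketamine, and is zero if discharge is equal between arms. All of this rests on assumed inpatient shares and correlations and on the borrowed 22.5/40.

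The missing pre-infusion VAS is a modest loss of precision (0.80 to 0.84 or 0.90 at an assumed correlation of 0.3 or 0.5, negligible at 0.1–0.2) with no bias. The absence of bias does not extend to the PACU timing: any PACU score taken before the infusion would pull that contrast toward zero, although there is no sign that this is intended. No gain from a baseline is claimed for McGill.

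**What to change.** In Outcome measures, replace the VAS sentence with: *VAS is recorded before the study drug infusion (from routine charting), after the infusion and before PACU discharge, and on POD1, POD2 and POD7 in every patient, by telephone if discharged.* Add that the PACU McGill is completed after the infusion.

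In both copies of the Statistical Analysis section, add: *VAS is analysed at post-infusion PACU, POD1, POD2 and POD7 with pre-infusion VAS as covariate; other inpatient VAS readings are descriptive.*

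The cost is one charted score per patient, VAS named on the existing telephone contacts, and a small protocol and CRF change. Some patients may be too drowsy to score before the infusion, so a rule for a missing covariate is needed (for example, the overall mean). If early and later pain are only weakly correlated, the covariate adds little, but fixing the days is still worthwhile.

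A minor editorial point can be settled in the same amendment. Overall study design and plan says "Patients are followed until the date of discharge" and describes one questionnaire completion after discharge. Outcome measures provides telephone contact for both POD2 and POD7, so a patient discharged before POD2 has two. The two sections should be reconciled.

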Potential subjects will have an initial pre-study screening, conducted by a member of the research team, to determine eligibility for the study. Potential subjects who are non-English speaking will be automatically excluded, because the questionnaires are copyrighted in English only. Subjects who do not have the capacity to consent will not be recruited. All other subjects will be recruited. For any patient who might be illiterate, consents will be read to him or her and witnessed by available staff or family member.

Informed Consent

Eligible patients will be assessed for capacity to give informed consent by a study team member. Medical clearance/status/stability will be addressed by members of the research team. Eligible patients will be invited to participate in the study. A verbal explanation of the study will be given followed by a written consent form. Study staff members are experienced at consenting patients for anesthesiology studies, and they include physicians as well as research associates.

[figure not shown]
Intervention Administration

Ketamine bolus doses of 0.4 mg/kg (by ideal body weight) will be prepared and stored by the Pharmacy staff at Tisch Hospital and will be delivered to the PACU on an on-call basis when required for a study subject. The study drug will be administered in accordance to best practices. Ketamine will be given via intravenous infusion through an IV line established in the PACU. All patients will have an IV line in the PACU as per standard postoperative care protocol after bariatric surgery. If necessary, an additional IV line will be placed by the study team for the infusion of the study drug. The study drug or control will be administered over <60 minutes. The dose for ketamine will be fixed at 0.4 mg/kg (ideal body weight). The staff administering the infusion will have no knowledge whether the agent is drug or saline control. The patient will be monitored in the PACU according to the standard PACU protocol. In addition, the patient will be monitored for any potential side effects of the medication, which include hypertension, tachycardia, nystagmus, perceptual disturbances, confusion, sedation, euphoria, dysphoria, and dizziness. These side effects are uncommon, and a majority of these side effects are expected to resolve shortly after infusion.¹³ Side effects will be documented and treated if necessary as per standard PACU protocol.

Study drug storage

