The Pharmacy at Tisch Hospital will randomize and prepare samples (study medication or saline control). Study medications and placebo will be kept by the Pharmacy staff at Tisch Hospital until use.

Main Study

Pharmacologic profile of study drug

Ketamine [(+/-)-2-(2-chlorophenyl)-2-(methylamino)-cyclohexanone] is a white, crystalline powder or clear liquid. It is a schedule III substance and is classified as a dissociative anesthetic. Ketamine is available as a racemic mixture with the S-(+)- isomer being more potent than the R-(-)- isomer. It is commercially supplied as the hydrochloride salt in 0.5 mg/mL and 5 mg/mL ketamine base equivalents. Clinically, it is commonly used as an anesthetic induction agent for diagnostic and surgical procedures prior to the administration of general anesthetics. It is also used as a low dose infusion for analgesia. For induction of 5-10 minutes surgical anesthesia, a dose of 1.0-4.5 mg/kg is intravenously administered; 6.5-13 mg/kg is given intramuscularly for 12-25 minutes of surgical anesthesia. As an analgesic, it is infused at a rate of 0.1 - 0.5 mg/kg/hr, with or without a loading dose.

The risks for ketamine are well studied. In general, ketamine is a well-tolerated medication. However, the following risks have been reported.

Pharmacokinetics: Bioavailability following an intramuscular dose is 93%, intranasal dose 25-50%, and oral dose 20±7%. Ketamine is rapidly distributed into brain and other highly perfused tissues, and is 12% bound in plasma. The plasma half-life is 2.3 ± 0.5 hours. Oral administration produces lower peak concentrations of ketamine, but increased amounts of the metabolites norketamine and dehydronorketamine. Ketamine and its metabolites undergo hydroxylation and conjugation. Norketamine produces effects similar to those of ketamine. There are no significant differences between the pharmacokinetic properties of the S-(+) and R-(-)-isomers.

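### PACU anti-emetic use is counted over the whole PACU stay, including doses given before the study drug, which dilutes a secondary comparison; the opioid window needs only a stated start.

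*Combined protocol and SAP*

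**What the plan says.** The secondary list under Outcome measures includes two outcomes confined to the PACU. Opioid use is an hourly rate, "opioid usage per hour during the PACU stay before and after ketamine infusion"; Specific aim 1 under Study Objective words it the same way. Anti-emetic use is "anti-emetic use in the PACU", with no starting point and no split. The plan does not say whether it is any use, a number of doses or an amount. Both come from the electronic chart.

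The section Overall study design and plan places the drug inside the PACU stay: "In the PACU, patients, if deemed medically stable by the study physician, will receive either 0.4mg/kg IV ketamine or placebo". Intervention Administration gives the length: "The study drug or control will be administered over <60 minutes".

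One item in the same list has an explicit anchor: "spirometry use 4 hours after the termination of ketamine infusion". The serum markers, listed separately as exploratory, are also timed from the end of the infusion. The opioid item has no such anchor. A further secondary outcome, "opioid usage per day throughout the hospital stay", covers opioid doses whenever they are given.

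**The concern.** An outcome meant to compare the arms should start when the arms begin to differ. Some PACU time must come before the study drug: the patient has first to be judged stable, and the plan's own before-infusion opioid rate presupposes such a period. Anti-emetics given in that period cannot respond to ketamine, yet the definition as written counts them.

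What is at stake is precision on one secondary outcome. It has some weight because the pharmacology section lists nausea and vomiting among ketamine's side effects, and no other listed outcome is aimed directly at them.

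The opioid item raises a smaller question. If *after* means after the end of the infusion, doses given during it (up to just under an hour) belong to neither rate. If it means after the start, nothing is left out. Two analysts could assign those doses differently and report different results from the same chart.

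**Working it through.** **The plan's own figure.** Neither PACU outcome has a sample-size calculation. The stated 50 per arm is for a 22.5% difference with SD 40%, power 0.8 and alpha 0.05 (taken as two-sided): 2 × (1.96 + 0.8416)² × (40/22.5)² = 49.6, so 50. It reproduces, and only n = 50 per arm is carried forward.

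**Anti-emetics as any use.** Let q be the share of patients dosed before the infusion, equal in both arms and independent of later use, and p₁, p₂ the shares dosed after it. Whole-stay use in arm i is 1 − (1 − q)(1 − pᵢ), so the whole-stay difference is (1 − q)(p₁ − p₂).

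The documents give no rates, so p₁ = 0.30, p₂ = 0.15 and q = 0.2 to 0.6 are assumptions. With h = 2 arcsin√a − 2 arcsin√b, where a and b are the whole-stay rates, and √(50/2) = 5, two-sided power is Φ(5h − 1.96) + Φ(−5h − 1.96):

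| q | whole-stay rates | difference | 5h | power |
|---|---|---|---|---|
| 0 | 30% v 15% | 15 points | 1.82 | 0.44 |
| 0.2 | 44% v 32% | 12 points | 1.24 | 0.24 |
| 0.4 | 58% v 49% | 9 points | 0.90 | 0.15 |
| 0.6 | 72% v 66% | 6 points | 0.65 | 0.10 |

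A larger assumed effect gives the same pattern. With 50% v 22% after the infusion and q = 0, 0.1, 0.3 and 0.5, the difference is 28, 25, 20 and 14 points, and power 0.84, 0.73, 0.50 and 0.32.

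**Anti-emetics as a dose count.** Earlier doses add equally to both means, so the difference is unchanged and only the variance grows. Borrowing the plan's standardized effect, 22.5/40 = 0.5625, and letting pre-infusion doses add a fraction f to the variance, power is Φ(5 × 0.5625/√(1 + f) − 1.96). For f = 0, 0.25, 0.5 and 1 this is 0.80, 0.71, 0.63 and 0.51.

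**Opioids: does leaving out the infusion period dilute?** Take *after* to mean after the end. Assume an infusion of T = 15 to 59 minutes and S = 1 to 4 hours in the PACU afterwards. Compare the hourly effect from the end of the infusion with that from its start, under two models.

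- *Constant effect from the start, stopping 45 minutes after the end.* This rests on "Effects generally last 30-45 minutes if injected". The ratio is (45/S) ÷ ((T + 45)/(T + S)), with S in minutes. T = 15, S = 60: 0.750/0.800 = 0.94. T = 59, S = 240: 0.1875/0.348 = 0.54. The after-end window loses effect.
- *Effect proportional to drug level.* This rests on "The plasma half-life is 2.3 ± 0.5 hours", with one compartment and a constant infusion rate; k = ln 2/2.3 = 0.301 per hour. For T = 59 minutes and S = 1 hour, the mean level is 0.525 of peak during the infusion and 0.863 after it; the mean from the start is (0.983 × 0.525 + 1 × 0.863)/1.983 = 0.695, and the ratio 0.863/0.695 = 1.24. For T = 15 minutes and S = 4 hours, it is 0.581/0.577 = 1.01. The after-end window loses nothing.

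The two models disagree on direction, and each starts from a figure in the protocol.

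**The case against.** A reader might infer that neither PACU window follows the drug and that both comparisons are diluted. The documents do not support this for opioids. The after-infusion rate is a separate quantity that does follow the drug, and the before-infusion rate can serve as a baseline. *After* is tied to neither end of the infusion, so an omission is only one possible reading. The spirometry and biomarker wording makes the end of infusion plausible but does not settle it. Even then, the direction of any loss is open: the 30–45 minute figure comes from a general list of routes of use, whereas the half-life and the rationale's hypothesis of long-lasting analgesia point the other way. Doses given during the infusion still enter the daily opioid outcome. This objection stands in full.

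A reader might also infer that the anti-emetic comparison is biased. It is not: pre-infusion doses are balanced in expectation by randomization and blinding.

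On size, it is fair to say that the plan never specifies any use, that all the rates are assumed, and that the undiluted power in the first illustration is only 0.44. Adverse events are also collected from patients and records, so nausea is not invisible elsewhere. These points limit the importance of the concern but do not remove it: under either definition, counting pre-drug doses costs power and gains nothing.

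**Conclusion.** The anti-emetic point holds. As written, the outcome includes doses that the study drug could not have affected. The loss is the factor (1 − q) on an any-use difference, or added variance on a dose count. In the main illustration, 15 points becomes 12 to 6 and power falls from 0.44 to between 0.24 and 0.10. Those figures rest on assumed rates, on pre-infusion use that is equal between arms and independent of later use, and on an any-use definition that the plan does not state. Only the direction is firm.

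For PACU opioid use, dilution is not shown. What remains is an unstated boundary: the plan should say where *after* begins.

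Severity is minor. Both are secondary outcomes, neither drives the sample size, and the consequence is lost precision.

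**What to change.** Define the anti-emetic outcome as use from the start of the study-drug infusion to PACU discharge, and state whether it is any use or a count. Report pre-infusion anti-emetic use separately by arm as a baseline descriptor.

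For PACU opioid use, add one sentence saying whether the after-infusion rate begins at the start or the end of the infusion, so that doses given during it have a fixed place. Settle this before unblinding, which means before the planned interim analysis at 50 completers, because that analysis includes the secondary endpoints.

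The cost is a few lines of wording and a filter on dose time. The data come from the electronic chart already in use, and the opioid split around the infusion already requires dose times. No extra visits, patients or measurements are needed.
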